8.3.2 ENDOSCOPY WITH BIOPSY AND EREFS

During post-screening endoscopies, biopsies will be obtained from the following locations:

- Distal esophagus (3-5 cm above the Z-line/squamo-columnar junction)
- Proximal esophagus (~15 cm above the Z line and within 10 cm of the esophageal inlet)

Up to 6 biopsies will be obtained from each location, focusing on areas of endoscopic abnormalities, if present. Additional details regarding biopsy collection, processing, and shipping instructions can be found in the MOP.

Endoscopic findings will be assessed by each investigator using the EoE Endoscopic Reference Score (EREFS)⁵⁰ in 5 classification categories: fixed rings, exudates, furrows, edema, and stricture.

8.6 UNSCHEDULED VISITS

If the need for a re-assessment of study samples and/or assessments occurs, an unscheduled visit may be scheduled to obtain an additional sample and/or assessment to analyze. In each instance, site should notify study monitor for approval of unscheduled visit.

8.7 SAFETY AND OTHER ASSESSMENTS

The following safety assessments will be performed:

1. Pregnancy test performed at every study visit for women of childbearing potential
2. Symptom assessment at every study visit
3. Adverse event assessment at every study visit, including injection site reactions
4. Vital signs as noted above with study drug administration
5. Adverse event review and assessment completed 48 hours after study drug administration
6. Month 8 visit occurring 3-months after last dose of study drug.
7. 30-day end of study phone call after study completion or early termination.

8.8 ADVERSE EVENTS AND SERIOUS ADVERSE EVENTS

8.8.1 DEFINITION OF ADVERSE EVENTS (AE)

Adverse event means any untoward medical occurrence associated with the use of an intervention in humans, whether or not considered intervention-related (21 CFR 312.32 (a)).

8.8.2 DEFINITION OF SERIOUS ADVERSE EVENTS (SAE)

An adverse event (AE) or suspected adverse reaction is considered "serious" if, in the view of either the site-investigator or sponsor (UNC), it results in any of the following outcomes: death, a life-threatening adverse event, inpatient hospitalization or prolongation of existing hospitalization, a persistent or significant incapacity or substantial disruption of the ability to conduct normal life functions, or a congenital anomaly/birth defect. Important medical events that may not result in death, be life-threatening, or require hospitalization may be considered serious when, based upon appropriate medical judgment, they may jeopardize the participant and may require medical or surgical intervention

to prevent one of the outcomes listed in this definition. Examples of such medical events include allergic bronchospasm requiring intensive treatment in an emergency room or at home, blood dyscrasias or convulsions that do not result in inpatient hospitalization, or the development of drug dependency or drug abuse.

8.8.3 ABNORMAL LABORATORY VALUES

In the event of unexplained abnormal laboratory test values which may be clinically significant, based on his/her medical judgment and the clinical setting, the site-investigator will determine whether to repeat the tests and should follow up as appropriate until they have returned to the normal range and/or an adequate explanation of the abnormality is found.

All abnormal laboratory values or test results should not necessarily be reported as AEs.

The criteria for determining whether an abnormal objective test finding should be reported as an AE include the following:

1. Test result is associated with accompanying symptoms (e.g., low red blood cell count [anemia] is accompanied by fatigue, shortness of breath, etc.)
2. Test result requires additional diagnostic testing or medical/surgical intervention
3. Test result leads to a change in study dosing or discontinuation from the trial, significant additional concomitant drug treatment or other therapy
4. Test result is considered to be an AE by the site-investigator or sponsor-investigator.

Merely repeating an abnormal test, in the absence of any of the above conditions, does not constitute an AE. Any abnormal test result that is determined to be an error should not be reported as an AE.

8.8.4 CLASSIFICATION OF AN ADVERSE EVENT

8.8.4.1 SEVERITY OF EVENT

This study will utilize the Common Terminology Criteria for Adverse Events (CTCAE), version 5.0 to assess all AEs. For AEs not included in the CTCAE grading system, the following criteria will be used to describe severity of the AE:

- **Grade 1** Mild; asymptomatic or mild symptoms; clinical or diagnostic observations only; intervention not indicated.
- **Grade 2** Moderate; minimal, local, or noninvasive intervention indicated; limiting age appropriate instrumental Activities of Daily Living (ADL). Instrumental ADL refer to preparing meals, shopping for groceries or clothes, using the telephone, managing money, etc.
- **Grade 3** Severe; medically significant but not immediately life-threatening; hospitalization or prolongation of hospitalization indicated; disabling; limiting self-care ADL. Self-care ADL refer to bathing, dressing and undressing, feeding self, using the toilet, taking medications, and not bedridden.
- **Grade 4** Life-threatening consequences; urgent intervention indicated.
- **Grade 5** Death related to AE.

8.8.4.2 RELATIONSHIP TO STUDY INTERVENTION

All AEs must have their relationship to study intervention assessed by an investigator who evaluates the event based on temporal relationship and his/her clinical judgment. The degree of certainty about

causality will be graded using the categories below. In a clinical trial, the study product must always be suspect.

- **Definitely Related** – There is clear evidence to suggest a causal relationship, and other possible contributing factors can be ruled out. The clinical event, including an abnormal laboratory test result, occurs in a plausible time relationship to study intervention administration and cannot be explained by concurrent disease or other drugs or chemicals. The response to withdrawal of the study intervention (dechallenge) should be clinically plausible. The event must be pharmacologically or phenomenologically definitive, with use of a satisfactory rechallenge procedure if necessary.
- **Possibly Related** – There is evidence to suggest a causal relationship, and the influence of other factors is unlikely. The clinical event, including an abnormal laboratory test result, occurs within a reasonable time after administration of the study intervention, is unlikely to be attributed to concurrent disease or other drugs or chemicals, and follows a clinically reasonable response on withdrawal (dechallenge). Rechallenge information is not required to fulfill this definition. “Possibly Related” means the reasonable possibility that the adverse event, incident, experience or outcome may have been associated with the procedures involved in the research (modified from the definition of associated with use of the drug in FDA regulations at 21 CFR 312.32(a)). Reasonable possibility means that the event is more likely than not related to participation in the research or, in other words, there is a >50% likelihood that the event is related to the research procedures.
- **Somewhat Likely to be Related** – There is some evidence to suggest a causal relationship (e.g., the event occurred within a reasonable time after administration of the trial medication). However, other factors may have contributed to the event (e.g., the participant’s clinical condition, other concomitant events) so there is a <50% likelihood that the event is related to the research procedures. Although an AE may rate only as “somewhat likely to be related” soon after discovery, it can be flagged as requiring more information and later be upgraded to “possibly related” or “definitely related”, as appropriate.
- **Unlikely to be Related** – A clinical event, including an abnormal laboratory test result, whose temporal relationship to study intervention administration makes a causal relationship improbable (e.g., the event did not occur within a reasonable time after administration of the study intervention) and in which other drugs or chemicals or underlying disease provides plausible explanations (e.g., the participant’s clinical condition, other concomitant treatments).
- **Not Related** – The AE is completely independent of study intervention administration, and/or evidence exists that the event is definitely related to another etiology. There must be an alternative, definitive etiology documented by the clinician.

8.8.4.3 EXPECTEDNESS

The site-investigator will be responsible for determining whether an AE is expected or unexpected. An AE will be considered unexpected if the nature, severity, or frequency of the event is not consistent with the risk information previously described for the study intervention.

8.8.5 TIME PERIOD AND FREQUENCY FOR EVENT ASSESSMENT AND FOLLOW-UP

The occurrence of an AE or SAE may come to the attention of study personnel during study visits and interviews of a study participant presenting for medical care, or upon review by a study monitor.

All AEs including local and systemic reactions not meeting the criteria for SAEs will be captured on the appropriate eCRF. Information to be collected includes event description, time of onset, investigator's assessment of severity, relationship to study product (assessed only by those with the training and authority to make a diagnosis), and time of resolution/stabilization of the event. All AEs occurring while on study must be documented appropriately regardless of relationship. All AEs will be followed to adequate resolution.

Any medical condition that is present at the time that the participant is screened will be considered as baseline and not reported as an AE. However, if the study participant's condition deteriorates at any time during the study, it will be recorded as an AE.

Changes in the severity of an AE will be documented to allow an assessment of the duration of the event at each level of severity to be performed. AEs characterized as intermittent require documentation of onset and duration of each episode.

Designated study staff will record all reportable events with start dates occurring any time after informed consent is obtained until 7 (for non-serious AEs) or 30 days (for SAEs) after the last day of study participation. At each study visit, the site-investigator or study site staff will inquire about the occurrence of AE/SAEs since the last visit. Events will be followed for outcome information until resolution or stabilization.

8.8.6 ADVERSE EVENT REPORTING

All AEs will be reported in a timely manner to the Lead Site via completion of an adverse event reporting eCRF. Additional information is provided in the MOP.

8.8.7 SERIOUS ADVERSE EVENT REPORTING

The site-investigator will immediately report to the sponsor any serious adverse event, whether or not considered study intervention related, including those listed in the protocol or investigator brochure and must include an assessment of whether there is a reasonable possibility that the study intervention caused the event. Study outcomes that are serious adverse events (e.g., all-cause mortality) must be reported in accordance with the protocol unless there is evidence suggesting a causal relationship between the study intervention and the event (e.g., death from anaphylaxis). In that case, the investigator must immediately report the event to the sponsor.

All SAEs will be followed until satisfactory resolution or until the site-investigator deems the event to be chronic or the participant is stable. Other supporting documentation of the event may be requested by the Data Coordinating Center (DCC)/study sponsor and should be provided as soon as possible.

The study sponsor will be responsible for notifying the FDA of any unexpected fatal or life-threatening suspected adverse reaction as soon as possible, but in no case later than 7 calendar days after the sponsor's initial receipt of the information. In addition, the sponsor must notify FDA and all participating investigators in an Investigational New Drug (IND) safety report of potential serious risks, from clinical trials or any other source, as soon as possible, but in no case later than 15 calendar days after the sponsor determines that the information qualifies for reporting.

8.8.8 REPORTING EVENTS TO PARTICIPANTS

Participants will be given any new information in a timely manner that may affect their willingness to continue participation and after approval from IRB.

8.8.9 EVENTS OF SPECIAL INTEREST

Events of special interest (ESI) must be reported within 24 hours of identification. Adverse events of special interest in this study include:

- Food impaction.
- Anaphylactic reactions or acute allergic reactions that require immediate treatment.
- Severe injection site reactions that last longer than 24 hours.
- Any severe infection, any bacterial infection requiring treatment with parenteral antibiotics or treatment with oral antibiotics for longer than 2 weeks, any clinical endoparasitosis, any opportunistic infection, any viral infection requiring antiviral treatment.

Note: Generally, all uncommon, atypical, peculiar, or unusually persistent infections, especially viral infections, should be reported as ESI.

8.8.10 REPORTING OF PREGNANCY

Pregnancy is not considered an AE unless there is a suspicion that an investigational product may have interfered with the effectiveness of a contraceptive medication. It is the responsibility of the site-investigator to report the event to the lead site within 24 hours of learning of the pregnancy. However, the outcome of all pregnancies (spontaneous miscarriage, elective termination, normal birth, or congenital abnormality) must be followed up and documented even if the subject was discontinued from the trial. If a subject becomes pregnant, they will also be withdrawn from the study.

All reports of congenital abnormalities/birth defects are SAEs. Spontaneous miscarriages should also be reported and handled as SAEs. Elective abortions without complications should not be handled as AEs. All outcomes of pregnancy must be reported to the Lead Site.

8.9 UNANTICIPATED PROBLEMS

8.9.1 DEFINITION OF UNANTICIPATED PROBLEMS (UP)

The Office for Human Research Protections (OHRP) considers unanticipated problems involving risks to participants or others (UPIRSO) to include, in general, any incident, experience, or outcome that meets all of the following criteria:

- Unexpected in terms of nature, severity, or frequency given (a) the research procedures that are described in the protocol-related documents, such as the Institutional Review Board (IRB)-approved research protocol and informed consent document; and (b) the characteristics of the participant population being studied;
- Related or possibly related to participation in the research (“Possibly related” means there is a reasonable possibility that the incident, experience, or outcome may have been caused by the procedures involved in the research. Reasonable possibility means that the event is more likely than not related to participation in the research or, in other words, there is a >50% likelihood that the event is related to the research procedures.); and
- Suggests that the research places participants or others at a greater risk of harm (including physical, psychological, economic, or social harm) than was previously known or recognized.

8.9.2 UNANTICIPATED PROBLEM REPORTING

The investigator will report unanticipated problems (UPs) to the reviewing IRB and to the DCC/study sponsor. The UP report will include the following information:

- Protocol identifying information: protocol title and number, investigator's name, and the IRB project number;
- A detailed description of the event, incident, experience, or outcome;
- An explanation of the basis for determining that the event, incident, experience, or outcome represents an UP;
- A description of any changes to the protocol or other corrective actions that have been taken or are proposed in response to the UP.

To satisfy the requirement for prompt reporting, UPs will be reported using the following timeline:

- UPs that are SAEs will be reported to the IRB and to the DCC/study sponsor within 24 hours of the investigator becoming aware of the event.
- Any other UP will be reported to the IRB and to the DCC/study sponsor within 24 hours of the investigator becoming aware of the problem.
- All UPs should be reported to appropriate institutional officials (as required by an institution's written reporting procedures), the supporting agency head (or designee), and the Office for Human Research Protections (OHRP) within the timeline specified per policy of the IRB's receipt of the report of the problem from the investigator.

8.9.3 REPORTING UNANTICIPATED PROBLEMS TO PARTICIPANTS

Participants will be given any new information in a timely manner that may affect their willingness to continue participation and after approval from IRB.

9 STATISTICAL CONSIDERATIONS

9.1 STATISTICAL HYPOTHESES

Primary Efficacy Outcome(s): Mean change in dysphagia from baseline to 3-months post-treatment (as measured by the EEsAI score with 7-day recall).

Hypothesis: Patients treated with mepolizumab will have lower EEsAI scores after 3-months of therapy compared to patients treated with placebo. Given the rapid mechanism of action of mepolizumab related to decreasing eosinophil counts, as well as recent clinical trial literature showing that dysphagia symptoms in EoE improve in a few as 8 weeks with both steroids and biologics, we feel that a 12 week course of mepolizumab is sufficient to demonstrate a symptom response.

Secondary Efficacy Outcome(s): Esophageal eosinophil counts in adults and adolescents with active eosinophilic esophagitis after a 3-month treatment course.

Hypothesis: Patients treated with mepolizumab will have lower esophageal eosinophil counts and higher rates of histologic response (defined with thresholds below 15 eosinophils per high-power field) compared to patients treated with placebo.

9.2 SAMPLE SIZE DETERMINATION

The study is powered for the primary outcome, the EEsAI score, which can range from 0-100, with a score of ≤ 20 indicating clinical remission, and a decrease of ≥ 20 points indicating a meaningful clinical response. Based on this, we estimate that with a sample size of 30 patients in each group we would be able to detect a difference in the mean change in EEsAI score of as little of 17, with a power of 0.9 at an α of 0.05, which would allow us to detect the clinically meaningful difference of 20 (see Table). Assuming a 20% dropout rate, we plan to randomize 36 patients in each group.

Table: Sample size considerations

Estimated mean decrease in EEsAI score after 12 weeks of treatment*				
Placebo	Mepolizumab	α	Power	N per group
10	30	0.05	0.9	22
15	30	0.05	0.9	38
20	30	0.05	0.9	85
10	35	0.05	0.9	14
15	35	0.05	0.9	22
15	32	0.05	0.9	30
20	35	0.05	0.9	38
10	40	0.05	0.9	10
15	40	0.05	0.9	14
20	40	0.05	0.9	22

*SD 20 for all

For the secondary outcome of proportion of patients with an EEsAI score ≤ 20 indicating clinical remission, a sample size of 30 in each group would allow us to detect as little as a 40% difference in remission rates between placebo and active therapy with a power of 0.9, a smaller difference that was detected in a recent trial using this metric.⁴⁸ This sample size would also provide ample power the for the absolute eosinophil count and EREFS secondary outcomes.

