5. Mean change in severity of endoscopic findings as measured by the EoE Endoscopic Reference Score (EREFS) from baseline to 3-months post-treatment.
6. Mean change in the Straumann Dysphagia Instrument (SDI) from baseline to 3-months post-treatment.

Prespecified Exploratory Outcomes

1. Mean change in peripheral blood eosinophil levels from baseline to 3-months post treatment.
2. For patients initially randomized to active medication, the same set of outcomes (as listed above) will be assessed after 6 months of treatment.
3. For patients initially randomized to placebo, a paired analysis will be conducted to compare month 6 to month 3 outcomes.
4. For the same set of outcomes (as listed above), 3-month data for patients initially randomized to active medication (300mg monthly) will be compared to 6 month data for patients initially randomized to placebo and who have completed 3-months of 100mg monthly. This will provide a comparison of the 300mg to the 100mg dose.
5. Adverse events and safety during all time points in the study.

Study Population:	72 adult and adolescent patients with active EoE as measured by both symptomatic and histologic severity.
Phase:	2
Description of Sites/Facilities Enrolling Participants:	4 United States sites. Competitive enrollment.
Description of Study Intervention:	Arm 1: Mepolizumab 300 mg SQ monthly for 6 months. Arm 2: Placebo SQ monthly for 3-months followed by mepolizumab 100mg SQ monthly for 3 months. (Note that both arms are blinded for the entire 6 months)
Study Duration:	3 years
Participant Duration:	10 months

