6.5.1 PROHIBITED TREATMENTS

No dietary changes, dilations, changes in baseline PPI medication dose, changes in inhaled or intranasal steroid doses, or administration or oral, topical/swallowed, or systemic steroids will be allowed during the study period (from consent through the end of treatment period). Esophageal dilation at the screening or month 3 endoscopy will result in study exit. However, dilation may be performed during or after the month 6 endoscopy, if clinically indicated.

If a subject has severe persistent or recurrent symptoms, or experiences a food impaction during the treatment period, rescue medications and procedures to treat EoE are allowed for clinical purposes. The sponsor will not supply rescue medications, and these would need to be prescribed as clinically indicated by the subject's physician. However, if such medications or treatments are required, the participant would be considered a treatment failure and would exit the study. If this happens, and at the discretion of the site-Investigator or sponsor-investigator it is safe and feasible to do so, the subject should return for an early termination visit.

Although the use of rescue medications is allowable at any time during the study, if safe and feasible to do so the use of rescue medications should be delayed until either the 3-month or 6-month assessments are completed. Rescue medications or treatments administered after the month 6 EGD will not result in study exit. The date and time of rescue medication administration as well as the name and dosage regimen of the rescue medication must be recorded.

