7 STUDY INTERVENTION DISCONTINUATION AND PARTICIPANT DISCONTINUATION/WITHDRAWAL

7.1 DISCONTINUATION OF STUDY INTERVENTION

Subjects may choose to withdraw from participation in the study at any time upon their request without penalty. Additionally, the investigator and sponsor may withdraw a subject from the study in the event of an intercurrent illness, adverse event (AE), treatment failure, protocol violation, cure, and for administrative or other reasons. Discontinuation from study treatment does NOT automatically lead to a complete withdrawal from the study. Subjects discontinuing from study treatment are strongly encouraged to complete early termination procedures and safety follow up.

Investigators should withdraw study treatment from subjects if any of the following occur:

- Pregnancy
- Lost to follow up
- Hypersensitivity / systemic allergic reaction to the study treatment requiring administration of epinephrine
- The subject meets an exclusion criterion (either newly developed or not previously recognized) that precludes further study participation

- Worsening symptoms or disease progression that, in the opinion of the investigator, requires either esophageal dilation or EoE treatment with either topical or systemic steroids during the treatment period
- Any adverse event that, in the opinion of the investigator, precludes safe continuation with the study protocol and study dosing
- Significant study intervention non-compliance, in the opinion of the investigator
- Any condition that, in the judgment of the site-PI or Sponsor, would compromise the ability of the patient to comply with the study protocol or complete the study

Before deciding to discontinue study treatment, the site-PIs should consult the Sponsor-Investigator and study medical monitor, regardless of the reason for discontinuation. Subjects who withdraw and have received at least 1 dose of study drug should return to complete the early termination visit.

The reason for participant discontinuation or withdrawal from the study will be recorded on the eCRF. Subjects who sign the informed consent form and are randomized but do not receive the study intervention may be replaced. Subjects who sign the informed consent form, and are randomized and receive the study intervention, and subsequently withdraw, or are withdrawn or discontinued from the study, will also be replaced such that the goal enrollment at the end of the study can be achieved.

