9.3 POPULATIONS FOR ANALYSES

The analysis dataset will be modified intention to treat (ITT), which will include all participants who received study drug and who have 3-month outcome data for EEsAI and endoscopy. We will have a secondary analysis dataset for a sensitivity analysis where the last available EEsAI value will be carried forward for any participants who terminate the study or are lost to follow-up.

The safety analysis dataset will be all participants who received study drug, regardless of follow-up time or other outcomes.

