9.4 STATISTICAL ANALYSES

9.4.1 GENERAL APPROACH

Descriptive statistics will be used to describe the data. Categorical variables will be presented as proportions and means will be presented with standard deviation and range. If the data are not normally distributed, medians and interquartile ranges will be presented rather than means, and non-parametric testing will be used. For inferential tests, a p value < 0.05 will be considered significant and all tests will be two tailed. All statistical estimates (e.g., medians, proportions, incidence rates, mean differences, correlations, etc.) will be tabulated along with corresponding confidence intervals (CIs).

Interpretation of CIs will play a major role as an integral part of the analysis of the data in concert with any statistical hypothesis tests. To avoid over-reliance on p-values, the magnitudes of estimates and the corresponding confidence intervals will be a focus of the analyses. Reasons for missing data will be investigated and recorded for purposes of statistical analyses. Because of the study design and outcome assessment, primary analyses will require exclusion of participants without outcome data. However, we will perform sensitivity analyses for missing data, initially assigning participants lost to follow up to treatment failure, then assigning them to treatment success and comparing the results, a technique that has been successful in prior clinical trials conducted by our group. For all outcomes, the null hypothesis is that there is no difference between the study groups. All hypothesis tests that are observed to be NOT statistically significant will be reported as being inconclusive.

The study statistician on this study will be [name].

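### Randomising 36 per group does not keep 30 evaluable at the stated 20% dropout, and sections 9.2 and 7.1 do not agree on the planned size (minor)

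*Combined protocol and SAP*

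**What the plan says.** Section 9.2 rests the primary power claim on 30 patients per group, a 17-point difference in mean EEsAI change and an SD of 20, "with a power of 0.9 at an α of 0.05". It then moves from 30 to the number randomised in one sentence: "Assuming a 20% dropout rate, we plan to randomize 36 patients in each group". It prints no formula for that step, gives no period for the 20%, and does not mention replacement. The synopsis (1.1) gives the study population as "72 adult and adolescent patients with active EoE as measured by both symptomatic and histologic severity", which agrees with 2 × 36.

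Section 9.3 limits the primary analysis set to "all participants who received study drug and who have 3-month outcome data for EEsAI and endoscopy", and 9.4.1 repeats that "primary analyses will require exclusion of participants without outcome data". Carrying the last value forward is a sensitivity analysis only.

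Section 7.1 deals with patients who were randomised and dosed and then leave. They "will also be replaced such that the goal enrollment at the end of the study can be achieved". Those randomised but never dosed may be replaced. The section gives the goal no number.

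**The concern.** A dropout allowance should leave the evaluable number on which the power rests. At 20% loss, 36 does not leave 30. Because 9.3 and 9.4.1 remove patients without month-3 data, losses before month 3 come straight off the primary analysis.

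Section 7.1 answers this in part and raises a second difficulty. If dosed withdrawals are replaced, the evaluable number recovers, but more than 36 per group are then randomised, and 9.2 describes 36 as the number to randomise. Read together, the two sections do not tell the reader whether 72 or some larger number will be randomised, or how many evaluable patients are planned. The DSMB meetings in 10.1.6 are set at fractions of the enrolment goal, so its definition has some practical use beyond the power statement.

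**Working it through.** **Inputs.** From 9.2: difference 17, SD 20, power 0.90, α 0.05, basis 30 per group, dropout 20%, 36 randomised per group, clinically meaningful difference 20. From 9.4.1: two-sided testing ("a p value < 0.05 will be considered significant and all tests will be two tailed").

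**Reproducing the plan's figure.** The two-sided normal formula is n per group = 2 × SD² × (1.960 + 1.2816)² / d².
- d = 17: 2 × 400 × 10.507 / 289 = 29.09, so 30.
- d = 20: 2 × 400 × 10.507 / 400 = 21.01, so 22.
- d = 10, 15, 25, 30: 84.06, 37.36, 13.45, 9.34, so 85, 38, 14, 10.

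All ten rows of the table in 9.2 reproduce. The basis of 30 is sound by the plan's own method.

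**The dropout step.**
- Left after 20% loss: 36 × 0.8 = 28.8 per group. This is below the stated 30 and slightly below the unrounded 29.09.
- Largest loss at which 36 still leaves 30: 1 − 30/36 = 16.7%.
- Number needed to keep 30 at 20% loss: 30/0.8 = 37.5, so 38.
- 30 × 1.2 = 36, so the figure may come from adding 20% to the evaluable number. No formula is printed, so this is an inference.

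**Timing of losses.** Only patients without month-3 data leave the primary analysis. Of the 36 × 0.2 = 7.2 losses per group, 1.2 (one in six) falling after the month-3 data would be enough to keep 30.

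**Power.** Power = Φ(d/SE − 1.960), with SE = 20 × √(2/n). SE is 5.270 at n = 28.8, 5.164 at 30 and 4.714 at 36. At 28.8, for example, 17/5.270 − 1.960 = 1.266, which gives 0.897. The t-test figures use the noncentral t with 2n − 2 degrees of freedom.

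| n per group | 17 points, normal / t | 20 points, normal / t | Difference detectable at 90% power, normal / t |
|---|---|---|---|
| 28.8 | 0.897 / 0.887 | 0.967 / 0.962 | 17.08 / 17.39 |
| 30 | 0.909 / 0.899 | 0.972 / 0.968 | 16.74 / 17.02 |
| 36 | 0.950 / 0.945 | 0.989 / 0.987 | 15.28 / 15.49 |

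The worst-case cost for 17 points is 1.1 power points (normal) or 1.25 (t). For 20 points the plan's table asks for 22 per group, which 36 keeps up to 1 − 22/36 = 38.9% loss.

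**What the replacement rule implies.** If replacements drop out at the same 20% (an assumption):
- no replacement: 72 randomised, 57.6 left, about 29 per group;
- 60 with month-3 data as the goal: 60/0.8 = 75 randomised, 30 per group;
- 72 remaining as the goal: 72/0.8 = 90 randomised, up to 36 per group.

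The figure of 60 is 2 × 30 from 9.2. No section states it as an enrolment goal.

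**The case against.** The strongest objection is that the shortfall needs two conditions that the protocol makes unlikely.

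First, it needs no replacement, whereas 7.1 says that dosed withdrawals will be replaced. That stands: the 28.8 is a worst case and departs from the plan as written. It does not settle the matter, because replacement means that 36 per group is not the number randomised.

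Second, it needs nearly all losses to come before month 3. The month-8 visit falls well after that, and 9.2 does not say over what period the 20% applies. Section 6.5.1 asks that rescue treatment be delayed, where safe and feasible, until the 3-month or 6-month assessments are done. It also says: "Esophageal dilation at the screening or month 3 endoscopy will result in study exit". A patient who exits at the month-3 endoscopy may already have the data that 9.3 requires. This stands too.

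Third, even the worst case agrees with 9.2 at its printed precision under the normal formula: 0.897 rounds to 0.9 and 17.08 to 17. The primary analysis is also an analysis of covariance on baseline EEsAI (9.4.2), which the table ignores. If 20 is the SD of change and the baseline and month-3 variances are equal (both assumptions), the residual SD is 20 × √((1 + ρ)/2). Power for 17 points at 28.8 per group is then about 0.98 at a correlation of 0.3, 0.94 at 0.7 and 0.91 at 0.9. This shows that the consequence is small, but it does not make 36 × 0.8 equal 30.

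Last, 72 is the only enrolment total in the documents and so the natural candidate for the goal in 7.1. That is fair, but no section makes the link, and 72 could mean randomised or remaining.

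**Conclusion.** The point holds as a minor correction. The 36 per group in 9.2 does not match its own 20% allowance from a basis of 30, and 9.2 and 7.1 do not agree on the planned size. Either 36 per group is the final number randomised, and 20% loss before month 3 leaves about 29, or losses are replaced and 36 is not the number randomised.

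A reader might infer that the trial is underpowered or that 38 per group must be randomised. The documents do not support either. The loss is at most about 1.1 to 1.25 power points for 17 points, and then only with no replacement and all losses before month 3. Power for the 20 points that 9.2 calls clinically meaningful stays at 0.962 to 0.967, and replacement under 7.1 to 30 or more evaluable per group removes the loss altogether. The trial's conclusion is not threatened. The power figures rest on the plan's SD of 20 and on equal groups.

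**What to change.** In 9.2, state that 36 per group retains 30 evaluable patients up to 16.7% loss before month 3. Add that at 20% loss it retains about 29, before any replacement under 7.1, with power of about 0.89 to 0.90 for 17 points and about 0.96 for 20.

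Reconcile 9.2 with 7.1 by saying whether 36 per group (72 in all) is the number randomised or the number remaining after replacement, and give the expected number randomised on that reading (about 90 if 72 are to remain at 20% loss). If the goal in 7.1 is instead a number with month-3 data, state that number and the number randomised that follows from it.

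The cost is one or two sentences in 9.2 and a clause in 7.1. The analysis does not change, and no added patients are needed for power.
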